12.2 Sponsor or regulatory monitoring

Trio Medicines, Ltd. (or their designee) or the relevant regulatory authorities may monitor/audit various aspects of the study. These monitors will be given access to facilities, databases, supplies and records to review and verify data pertinent to the study.

12.3 Record retention

The sponsor and both principal investigators will keep the following in a trial master file.

- All the essential documents required by GCP
- All data generated during the study

All documents will be stored such that they are readily available for inspection at the request of the sponsor or a regulatory authority. Any transfer of ownership of the investigator's data or documents will be documented, and the sponsor will be informed.

For at least 15 years after the end of the study, and at least 2 years after the last approval of a marketing application in an ICH region and until there are no pending or contemplated marketing applications in an ICH region or at least two years have elapsed since the formal discontinuation of clinical development of the study medication:

- HMR will ensure that the sponsor's master file and original copies of CRFs will be archived in a secure place; and
- the investigators will ensure that the investigator's master file, and original source documents (other than CRFs) will be archived in a secure place.

12.4 Clinical Trial Agreement

The sponsor and the investigators will sign an agreement outlining each party's obligations with respect to the trial.

Each party will allow the other 30 days to comment before any results are submitted for publication, or 10 days prior to an abstract presentation. Authorship should reflect work done by the investigators and personnel of the sponsor, in accordance with generally recognized principles of scientific collaboration.

13 Statistical methods

13.1 Analysis Sets

The safety analysis set will include all patients who are randomized and receive at least one dose of study medication. In this population, treatment will be assigned based upon the treatment patients actually receive regardless of the treatment to which they were randomized.

The pharmacokinetic analysis set will include all patients who receive at least one dose of study medication, and yield at least one plasma concentration for YF476.

The Intent-to-Treat (ITT) analysis set will include all randomized patients who receive at least one dose of study medication and have at least one post-baseline assessment. In this population, treatment will be assigned based upon the treatment to which patients were randomized regardless of which treatment they actually received.

A per-protocol analysis will also be completed.

13.2 General Statistical Considerations

The null hypothesis is that there is no difference between YF476 and placebo in the treatment of patients with Barrett's esophagus, the alternative hypothesis is that there is a difference between the treatments. Statistical significance will be defined as $p \leq 0.05$.

Statistical analysis will be done by HMR. The statistical package SAS (version 9.2) will be used to produce all summary tables and data listings.

For the data analysis, missing or dropout data will not be imputed; analyses will be performed only on observed data. In this study, there will be no significance level adjustment for multiplicity.

Quantitative data will be tabulated with descriptive summary statistics: arithmetic mean, standard deviation, median, minimum and maximum values, and number of observations. Geometric mean and geometric CV% will be provided for C_{\max} and C_{trough} . For categorical data, frequency tables will be provided.

A detailed Statistical Analysis Plan (SAP) describing the methodology to be used in the final analysis will be prepared by the HMR Statistics and Data Management Department after completion of the final protocol. Any deviations from the planned statistical analyses in the protocol will be fully described in the SAP.

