9.1 **Primary endpoint**

- Change in Ki67 expression (Δ Ki67) between baseline (Visit 2) and the Week 12 visit

9.2 **Secondary endpoints**

- Biomarkers
 - Change from baseline at Week 12 in biomarkers potentially associated with esophageal adenocarcinoma, in particular:
 - Change in CCK2R mRNA levels
 - Change in DCAMKL1 expression

- Change in DCAMKL1 mRNA levels
- Change in COX-2 mRNA levels
- Change in p53 expression
- Gene expression will be measured using RNA-Seq. Further examination of any changes in expression from baseline may be done using qRT-PCR and IHC.
- Reduction in PPI-induced increase in plasma CgA
- Increase in PPI-induced hypergastrinaemia
- Safety
 - Vital signs, ECG, physical examination, laboratory safety tests: blood tests: red blood cells (RBC), haemoglobin, haematocrit, platelets, white blood cells (WBC, differential: neutrophils, bands, lymphocytes, monocytes, eosinophils, basophils), sodium, potassium, magnesium, chloride, bicarbonate, creatinine, serum glucose, blood urea nitrogen (BUN), alkaline phosphatase, lactate dehydrogenase (LDH), serum glutamic-oxaloacetic transaminase/aspartate amino transferase (SGOT/AST), serum glutamic-pyruvic transaminase/ alanine aminotransferase (SGPT/ALT), total bilirubin, total protein, albumin, calcium, amylase, lipase; and urine tests: pH, specific gravity, protein, glucose, ketones, blood.
 - Change in histology
- Tolerability: assessment of adverse events.
- Pharmacokinetics: through and peak concentration of YF476

10 Methods

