10.2 Rationale for laboratory methods

In general, it is desirable to perform quantitative analyses of biomarkers, as achieved by using quantitative real-time PCR (qRT-PCR), in contrast to qualitative or semi-quantitative immunohistochemical analyses (IHC). Quantitative analysis allows for detection of small differences between different tissue samples. However, qRT-PCR does not discriminate between different cell types within a particular tissue sample, whereas IHC allows for visual assessment of the type and location of cells that express a biomarker of interest. We will also employ RNA-Seq (RNA sequencing) to identify changes in gene expression caused by treatment with netazepide in Barrett's esophagus tissue.

- IHC for Ki67 is a robust marker of ongoing proliferation, and has been reliably and reproducibly used to evaluate cell type-specific evaluation. Quantitative assessment of the number of proliferating (Ki67+) epithelial cells is easiest and most reliable in IHC.
- For the assessment of CCK2R expression in human esophageal tissue, qRT-PCR seems to be the best method, as IHC with various antibodies has proven to be unreliable and non-specific.
- Biologically relevant COX-2 expression can be quantitatively assessed using qRT-PCR, but cannot be detected by IHC.
- DCAMKL-1 is a putative marker of intestinal stem cells. In order to analyze expansion of these putative stem cells in the development of Barrett's esophagus, it is important to get an impression of the precise location of these cells. Therefore, both qRT-PCR and IHC will be used to analyze DCAMKL-1 expression.
- Changes in the levels of p53 protein expression can be detected best with IHC, as mRNA levels of p53 do not differ very much despite altered protein expression. The function of p53 is more likely determined by protein stability.
- RNA-Seq is an untargeted approach to studying changes in gene expression; this is particularly valuable in the current study, as the effects of gastrin receptor antagonism in Barrett's esophagus tissue with regard to esophageal adenocarcinoma prevention are unknown.

In order to identify other key pathways impacted by gastrin receptor antagonism in BE, we will do RNA-Seq to assess the difference in gene expression between the netazepide and placebo groups. In addition to the original focus aimed at assessing expression of a very limited number of genes, this analysis will serve to identify affected pathways in

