the progression from Barrett's esophagus to esophageal adenocarcinoma, potential prognostic markers, and possible new chemopreventive targets.

All the above described methods have been performed in previously published studies (by the chief investigator's group and others) as well as in [name] laboratory in a new mouse model of Barrett's esophagus and adenocarcinoma.

Therefore, the investigators will be able to compare the achieved data with previously published and unpublished results from the chief investigator's laboratory and other groups.

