13.4 Efficacy Analyses

All efficacy analyses, summaries and listings will be generated using the efficacy analysis set.

Primary efficacy variables are:

- Change in Ki67 expression (ΔKi67)

Secondary efficacy variables are:

- Changes in gene expression in BE tissue (measured by RNA-Seq).
- Change in CCK2R mRNA levels (measured by qRT-PCR)
- Change in DCAMKL1 expression (measured by IHC)
- Change in DCAMKL1 mRNA levels (measured by qRT-PCR)
- Change in COX-2 mRNA levels (measured by qRT-PCR)
- Change in p53 expression (measured by IHC)
- Change in serum gastrin and plasma CgA between baseline and Visit 5

For all efficacy variables listed above, individual values will be presented by patient and summarised by visit.

The primary endpoint (Change from baseline (Visit 2) in Ki67 expression (Δ Ki67)) will be summarised using descriptive statistics. The primary analysis for the primary endpoint will use two sample t-tests comparing between treatment groups. Nominal p-value and 95% confidence intervals for treatment difference will be reported.

To evaluate the robustness of the primary analysis, the following sensitivity analysis will also be performed:

Baseline Adjusted Analysis: this sensitivity analysis will use an analysis of covariance model with the primary endpoint as the dependent variable, treatment group as a factor and baseline (Visit 2) as a covariate. Adjusted least square means and corresponding 95% confidence interval will be reported.

Serum gastrin and chromogranin A (CgA) will be measured at baseline (Visit 2) and at Weeks 6 and 12. Analyses will be performed to determine whether there is a correlation between baseline gastrin and subsequent Δ Ki67. YF476 assays will be performed at Weeks 6 and 12.

Analysis of the secondary endpoints will be similar to the primary analysis. No sensitivity analysis is planned for these endpoints.

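### The study-wide rule of p ≤ 0.05 without multiplicity adjustment has no exception for untargeted RNA-Seq, and neither document supplies an RNA-Seq method

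*Protocol*

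**What the plan says.** **Testing rules.** Protocol 13.2 puts the significance threshold at p ≤ 0.05 and adds "In this study, there will be no significance level adjustment for multiplicity". It names no exception. Protocol 13.4 places RNA-Seq first among the secondary efficacy variables, in an entry that begins "Changes in gene expression in BE tissue (measured by RNA-Seq". The same section makes a two-sample t-test with a nominal p-value the primary analysis of Ki67, and then says "Analysis of the secondary endpoints will be similar to the primary analysis".

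**Purpose of RNA-Seq.** Protocol 10.2 says "RNA-Seq is an untargeted approach to studying changes in gene expression" and "we will do RNA-Seq to assess the difference in gene expression between the netazepide and placebo groups". The intended products include affected pathways, "potential prognostic markers, and possible new chemopreventive targets". Protocol 9.2 makes laboratory confirmation optional: "Further examination of any changes in expression from baseline may be done using qRT-PCR and IHC".

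**Where the method should be written down.** Protocol 13.2 calls for a detailed SAP setting out the methods of the final analysis, and promises "Any deviations from the planned statistical analyses in the protocol will be fully described in the SAP". Protocol 7.7 allows study-wide unblinding only after the SAP is signed and the database locked.

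**What the SAP does.** SAP 3 excludes efficacy data, which are to be reported separately, and then brings serum gastrin and plasma CgA back in. SAP 4.2.2 keeps RNA-Seq among the secondary endpoints. SAP 4.3 says, without qualification, that there will be no formal testing. SAP 15 summarises gastrin and CgA descriptively. SAP 17 lists one departure from the protocol, the dropped pharmacokinetic analysis set.

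**The concern.** The rules in Protocol 13.2 and 13.4 fit the short list of named markers, where each nominal p-value can be read on its own. RNA-Seq is different in kind, because one endpoint carries thousands of comparisons. With no exception, gene filter, model or error rate stated, the only rule on paper is the one written for single markers. A gene list produced under it would be mostly noise if few genes respond. It could be reported as pathways, prognostic markers or drug targets without confirmation, since follow-up by qRT-PCR or IHC is discretionary.

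The second issue is timing. The protocol relies on the signed SAP to fix methods before the blind is broken. This SAP does not do so for RNA-Seq and cites no other plan that does.

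A smaller gap concerns the tissue. Protocol 10.1 and 10.3.2 take two study biopsies each from the GE junction, the mid-Barrett's segment and normal esophagus. Protocol 13.4 speaks only of BE tissue and does not name the site to be analysed.

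**Working it through.** **1. Inputs from the documents.** Threshold 0.05, two-sided; 10 patients per arm (Protocol 13.2, 13.7). Primary test: two-sample t-test (Protocol 13.4). The number of genes is not stated anywhere, so every gene count below is an assumption.

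**2. Reproducing the plan's own figure.** Two-sample t-test power uses noncentrality δ / (SD × √(2/n)) with 2n − 2 = 18 degrees of freedom. For a difference of 0.30, SD 0.16 and n = 10, the noncentrality is 0.30 / (0.16 × 0.4472) = 4.19 and power is 97.7%, against 98% stated. Other cells of Table 1 also agree: 96.5% (97% stated) for 0.25/0.14, 91.0% (91%) for 0.25/0.16, 83.6% (84%) for 0.25/0.18, 94.1% (94%) for 0.30/0.18 and 98.4% (98%) for 0.35/0.18. The Ki67 power calculation is sound, and the same t-test machinery is used below.

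**3. Named markers only.** Protocol 13.4 names seven secondary tests besides RNA-Seq: CCK2R mRNA, DCAMKL1 by IHC, DCAMKL1 mRNA, COX-2 mRNA, p53, gastrin and CgA. If all were null, the expected number of false calls is 7 × 0.05 = 0.35. The chance of at least one, assuming independence, is 1 − 0.95^7 = 30.2%. For a pilot with p-values read as nominal, that is tolerable.

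**4. The same rule applied gene by gene.** Expected false calls = 0.05 × number of null genes:

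| Assumed null genes | Expected false calls |
|---|---|
| 5,000 | 250 |
| 10,000 | 500 |
| 20,000 | 1,000 |

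**5. Effect of false discovery rate control (illustration).** Assume 10,000 independent, normally distributed genes, 10 patients per arm, and one common effect size for all responding genes. Power at nominal 0.05 is 56.2% for a 1 SD effect and 98.8% for 2 SD. With 10% responding, nominal testing gives 1,000 × 0.562 = 562 or 1,000 × 0.988 = 988 true calls, and 9,000 × 0.05 = 450 false calls. The Benjamini-Hochberg results are means over 100 simulated trials:

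| Scenario | Nominal 0.05: true / false | Benjamini-Hochberg 5%: true / false |
|---|---|---|
| No genes respond | 0 / about 500 | 0 / 0.02 |
| 10% respond, 1 SD | 562 / 450 | 21.1 / 1.2 |
| 10% respond, 2 SD | 988 / 450 | 870.9 / 42.1 |

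The false share of all nominal calls is 450/1,012 = 44% at 1 SD and 450/1,438 = 31% at 2 SD. With Benjamini-Hochberg it is 1.2/22.3 = 5% and 42.1/913.0 = 5%.

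**6. Gastrin and CgA, side by side.** Protocol 13.4 lists them as secondary variables and so plans primary-style comparisons between arms. SAP 15 summarises them by group and visit with no comparison. SAP 17 does not list the change, although Protocol 13.2 and SAP 3 both promise that such differences will be identified.

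**The case against.** Several points on the other side have force.

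- **Gene-by-gene t-tests are nowhere prescribed.** A reader might infer that the protocol orders them. It does not: it says secondary analyses will be similar to the primary, and it asks for individual values by patient and summaries by visit, which suits single markers. The t-test per gene is only what the written rules give if carried over. This stands, and it makes the figures conditional.
- **The SAP need not contradict the protocol on RNA-Seq.** A reader might infer from SAP 4.3 that no gene will be tested. But SAP 3 sends tissue efficacy data elsewhere, so 4.3 can be read as covering only what the SAP itself analyses. The documents do not support a firm contradiction for RNA-Seq. The scope of 4.3 is still unclear, because the SAP also repeats the Ki67 power table (8.1) and names the population for analysing the primary endpoint (9). For gastrin and CgA, which are in the SAP's scope, the departure is real and unlisted.
- **Pre-specification is required.** A reader might infer that the RNA-Seq method may be left until after unblinding. Protocol 13.2 and 7.7 together say otherwise. The fair criticism is that this SAP does not deliver what they call for.
- **This is a pilot, and RNA-Seq is framed as discovery.** Protocol 10.2 speaks of potential markers and possible targets. That lowers the stakes, but 13.4 still lists RNA-Seq as a secondary efficacy variable, not as exploratory.
- **A separate efficacy plan may exist.** That cannot be checked; neither document gives or cites one.
- **The biopsy site is a small matter.** Normal esophagus is clearly distinguished from the mid-Barrett's segment, so the main ambiguity is the GE junction.

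**Conclusion.** The point holds in a limited form. The protocol's no-adjustment rule covers the RNA-Seq comparison as worded, no exception or error-control method appears in either document, and the SAP that should contain the method does not. If the written rules were followed gene by gene, about 250 to 1,000 false calls would be expected for an assumed 5,000 to 20,000 null genes. The illustration also assumes independence, normality and one common effect size, so it shows the scale of the problem and does not predict this trial's results.

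The gastrin and CgA departure is a separate, smaller defect of documentation. The Ki67 test and its power are untouched, and nominal p-values remain defensible for the few named markers in a pilot. This should be corrected before unblinding, but it does not threaten the primary conclusion.

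**What to change.** 1. In Protocol 13.2 and 13.4, exempt RNA-Seq from the no-adjustment and similar-to-primary rules, and label it exploratory.
2. Before unblinding, specify in the SAP, or in an efficacy plan that it cross-references, a gene-wise model of baseline-to-Week-12 change by treatment in a named Barrett's biopsy site, with false discovery rate control (for example Benjamini-Hochberg at 5%). The alternative is a ranked gene list with no significance claims.
3. State which data SAP 4.3 covers.
4. For gastrin and CgA, either restore the between-arm comparisons at nominal p-values or record their removal, with the reason, in SAP 17. Limiting 4.3 to the SAP's own data would not settle this, because it would confirm no testing for exactly these two markers.
5. Leave Ki67 and the other named markers at nominal p-values.

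The drafting cost is a few short paragraphs, and the software is standard. The scientific cost is fewer genes declared significant: in the illustration, true calls fall from 988 to about 871 at 2 SD and from 562 to about 21 at 1 SD. If the loss at modest effects is unacceptable, the ranked list avoids it by making no significance claims.

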13.3 Study Population Data

The safety population will be summarized for demographic characteristics, and will be presented. Continuous demographic variables (age, weight, height, and BMI) will be summarised with descriptive statistics. Categorical demographic variables (gender, race, and ethnicity) will be summarised with frequency counts and corresponding percentages.

13.4 Efficacy Analyses

All efficacy analyses, summaries and listings will be generated using the efficacy analysis set.

Primary efficacy variables are:

- Change in Ki67 expression (ΔKi67)

Secondary efficacy variables are:

- Changes in gene expression in BE tissue (measured by RNA-Seq).
- Change in CCK2R mRNA levels (measured by qRT-PCR)
- Change in DCAMKL1 expression (measured by IHC)
- Change in DCAMKL1 mRNA levels (measured by qRT-PCR)
- Change in COX-2 mRNA levels (measured by qRT-PCR)
- Change in p53 expression (measured by IHC)
- Change in serum gastrin and plasma CgA between baseline and Visit 5

For all efficacy variables listed above, individual values will be presented by patient and summarised by visit.

The primary endpoint (Change from baseline (Visit 2) in Ki67 expression (Δ Ki67)) will be summarised using descriptive statistics. The primary analysis for the primary endpoint will use two sample t-tests comparing between treatment groups. Nominal p-value and 95% confidence intervals for treatment difference will be reported.

To evaluate the robustness of the primary analysis, the following sensitivity analysis will also be performed:

Baseline Adjusted Analysis: this sensitivity analysis will use an analysis of covariance model with the primary endpoint as the dependent variable, treatment group as a factor and baseline (Visit 2) as a covariate. Adjusted least square means and corresponding 95% confidence interval will be reported.

Serum gastrin and chromogranin A (CgA) will be measured at baseline (Visit 2) and at Weeks 6 and 12. Analyses will be performed to determine whether there is a correlation between baseline gastrin and subsequent Δ Ki67. YF476 assays will be performed at Weeks 6 and 12.

Analysis of the secondary endpoints will be similar to the primary analysis. No sensitivity analysis is planned for these endpoints.

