3.3 Rationale

As described above, clinical guidelines for the management of BE include gastric acid suppression with chronic PPI therapy. Acid reflux appears to have an important causal role in the development of BE, and a history of reflux symptoms is associated with EAC.¹² However, data are inconclusive with regard to acid suppression and EAC risk. In a retrospective study of veterans with BE, PPI compared with histamine- H_2 antagonists or no acid suppression was associated with a lower risk of progression to dysplasia.¹³ In contrast, other studies suggest that PPIs may be associated with an *increased* risk for developing EAC,¹⁴ and Feagins *et al* reported anti-proliferative effects of acid exposure in non-dysplastic BE cells.¹⁵

By inhibiting acid secretion, PPIs at therapeutic doses can cause secondary hypergastrinemia. Gastrin exerts trophic effects in BE via CCK2R activation.⁵ There is increased expression of CCK2R in BE compared to squamous epithelium, and gastrin can stimulate proliferation, anti-apoptosis, COX-2 expression, and loss of cell-cell adhesion in BE cells.^{5, 16} The chief investigator's group recently reported that BE patients with high serum gastrin levels had significantly increased odds of a history of high grade dysplasia (HGD) or EAC.⁶ In that cross-sectional study, they enrolled 95

patients with BE (with and without dysplasia or EAC) and GERD controls on chronic PPI therapy. Subjects in the highest serum gastrin quartile had significantly increased odds of a history of advanced neoplasia (adjusted OR 5.46, 95% CI 1.20–24.8). The group also analyzed 19 samples from non-dysplastic Barrett's epithelium, and found marked elevations in Ki67 expression, with a mean Ki67 index of 48.3% (SD 16.0%). They also found a moderate correlation between serum gastrin and tissue Ki67 index ($r=0.64$, $p=0.05$) in a subset of ten patients¹⁷.

Those studies support the notion that gastrin may promote carcinogenesis in BE, and that these potentially pro-neoplastic effects occur via activation of the CCK2 receptor. We therefore propose the following clinical trial to analyze the effects of a CCK2 receptor antagonist in patients with BE. The primary hypothesis is that administration of YF476, a CCK2 receptor antagonist, in patients with BE will result in a significant decrease in cellular proliferation in the Barrett's mucosa.

4 Summary of study plan

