7.6 Registration and randomization

- A member of the HMR Statistics and Data Management Department will generate a randomization list for each site. Patient numbers will be allocated to eligible patients immediately before the EGD and biopsy at Visit 2 (Baseline). Patients enrolled at CUMC will be allocated patient numbers 01–24. Patients enrolled at NIHR CIW will be allocated patient numbers 1001–1024. The lists are independent of each other. At both sites, patients on PPI once daily will be given the next available number from the top of the list, and patients on PPI twice daily will be given the next available number from the bottom of the list.
- At each site, the site coordinators will maintain a site-specific list of participants, including patient codes, start date, and duration of treatment. Every time a patient is recruited at one of the sites, the coordinator for that site will inform the chief investigator (if applicable) and the coordinator for the other site. It is the chief investigator's responsibility to ensure that the total number of study patients does not exceed the target.

The randomization list will specify whether the patient receives a dose of YF476 or placebo. Fixed allocation randomization will be performed, with equal allocation (1:1) between the 25 mg YF476 and placebo groups. Blocked randomization will be used. Randomization will be stratified by PPI dose and by site. The site pharmacy will dispense YF476 or placebo according to the randomization list. The study investigators and the study patients will remain blinded.

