7.7 Blinding and unblinding methods

- Bottles containing study medication for individual patients will not be labelled with any information to indicate whether the capsules are YF476 or placebo.
- Patients will be blinded to study treatment.
- One member of the HMR Statistics and Data Management Department will not be blinded. That person will generate the randomization code. The Columbia University biostatistician will be blinded.
- All Investigators will be blinded to study treatment.

-
- For each site, there will be a blinded monitor and an unblinded monitor. The unblinded monitor will review dispensing records at the site Pharmacy.
 - Pharmacy staff will not be blinded.
 - The Data and Safety Monitoring Board will not be blinded.
 - The blind will be broken by the investigator or delegate in the following circumstances:
 - If unblinding is required in the interest of the safety of a subject, an investigator will discuss the matter with the sponsor before opening the individual code-break envelope for that subject. In a medical emergency, the principal investigator or delegate may open the individual code-break envelope for that subject without prior consultation with the sponsor. In that event, the principal investigator or delegate will notify the sponsor as soon as possible that the randomisation code has been broken for the subject.
 - The blind will be broken for the entire study population at the completion of the study, after the statistical analysis plan (SAP) has been signed and the database has been locked.

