13.7 Determination of sample size

Based on our preliminary data, we estimate a mean baseline Ki67 index of 45–50%, with a common SD of 14–18%. Assuming a two-sided type I error rate of 0.05, a sample size of 20 (10 per arm) has 98% power to detect a 30% absolute difference in $\Delta Ki67$ between the two arms if the common SD is 16%, and 97% power for a 25% difference with a 14% common SD (see Table 1).

Table 1. Power calculations based on 20 patients (10 per arm)			
	$\Delta\text{Ki67}_{\text{YF}} - \Delta\text{Ki67}_{\text{pl}}$		
SD	0.25	0.30	0.35
0.14	97%	99%	>99%
0.16	91%	98%	>99%
0.18	84%	94%	98%

14 Ethical and regulatory considerations

This trial will be conducted in compliance with the protocol, Good Clinical Practice (GCP), and the applicable regulatory requirements.

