### **3 Introduction**

This Statistical Analysis Plan (SAP) is based on the current trial protocol (version 24, 26 April 2018). Where statistical methods differ substantially between this SAP and the protocol, that will be identified in this document.

This SAP describes the datasets and the statistical methods to be used for the reporting and analysis of all data collected during the trial except the efficacy data which will be reported separately. Serum gastrin and plasma CgA data will be included in this SAP.

The randomisation code will not be broken before this SAP is finalised. If a future protocol amendment necessitates a substantial change to the statistical analysis of the trial data, this SAP will be amended accordingly. If, after database lock, additional analyses are required to supplement the planned analyses described in this SAP, those unplanned analyses will not be described in an amended SAP, but they will be identified in the integrated clinical study report (CSR). Any deviations from this SAP will be documented in the CSR.

This SAP has been written in consideration of the following guidelines:

- International Conference on Harmonization (ICH) E9, Guidance for Industry: Statistical Principles for Clinical Trials (ICH E9 1998); and
- ICH E3, Guidance for Industry: Structure and Content of Clinical Study Reports (ICH E3 1995).

Statistical analysis will be done using SAS® 9.3 on a Windows PC.

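### The primary Ki67 analysis is an unadjusted t-test on change; the baseline ANCOVA already planned, likely more precise with 10 per arm, should take its place

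*Protocol*

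**What the plan says.** Protocol 13.4 defines the primary variable as change in Ki67 from Visit 2 to Week 12 and continues: "The primary analysis for the primary endpoint will use two sample t-tests comparing between treatment groups". For that test it promises a p-value and a 95% confidence interval for the treatment difference.

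The baseline-adjusted model comes second: "this sensitivity analysis will use an analysis of covariance model with the primary endpoint as the dependent variable", with treatment as a factor and baseline Ki67 as covariate. Its output is described only as follows: "Adjusted least square means and corresponding 95% confidence interval will be reported". No adjusted difference or p-value is named.

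Protocol 13.7 bases the trial size on the unadjusted comparison: "a sample size of 20 (10 per arm) has 98% power to detect a 30% absolute difference", at an SD of 16%. Protocol 7.6 says "Randomization will be stratified by PPI dose and by site", but neither Ki67 model in 13.4 contains those factors.

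The SAP does not replace this plan. Its Introduction says it covers "all data collected during the trial except the efficacy data which will be reported separately", apart from gastrin and CgA. Section 9 names the ITT population for the primary endpoint, section 4.3 says there will be no formal testing, and section 17 lists no change to the Ki67 analysis. The document governing the separate efficacy report was not available for this review.

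**The concern.** A change score subtracts the whole baseline value, which fixes the slope of Week 12 on baseline at 1. ANCOVA estimates that slope. When the true slope is below 1, as regression to the mean usually makes it, the change score over-corrects and carries extra noise.

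Two things are at stake in a 20-patient trial. One is precision: the primary interval may be wider than the collected data require. The other is chance imbalance. Randomization is not stratified on baseline Ki67, so one arm may start higher, and the t-test on change then credits that arm with part of its regression to the mean. Both methods are unbiased over repeated trials, but only one trial will be run. As the plan stands, the t-test governs if the two analyses disagree.

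**Working it through.** **Inputs.** 10 per arm and two-sided 0.05 (Protocol 13.7). SD 14 to 18 points and differences of 25 to 35 points (Table 1). Single-time-point SD 16.0% from 19 samples (Protocol 3.3). The baseline/Week 12 correlation r and the Week 12 SD are not given, so both are varied.

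**1. The plan's own figures.** Noncentral-t power with 18 df reproduces Table 1 within 2 percentage points in every cell. Examples are 97.7% for 30 points at SD 16 (stated 98%), 96.5% for 25 at SD 14 (97%) and 83.6% for 25 at SD 18 (84%). Table 1 is therefore t-test power, with the tabled SD acting as the SD of change.

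**2. The implied correlation.** With equal SDs, SD of change = SD x sqrt(2(1 - r)). Using 16 on both sides, 16 = 16 x sqrt(2(1 - r)), so r = 0.5.

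**3. Variance ratio.** The ANCOVA residual SD is SD x sqrt(1 - r²). Estimating the slope inflates the variance by 1 + 1/(20 - 4) = 1.0625 on average. With equal SDs the ratio of ANCOVA to t-test variance is 1.0625 x (1 + r)/2, which at r = 0.5 is 1.0625 x 0.75 = 0.797. Interval width also pays for 17 rather than 18 df, and break-even is then at r of about 0.87.

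**4. Width and power, SD 16 at both visits.** Simulation from a bivariate normal model (100,000 trials per setting) agrees with the formulas. Null rejection is 4.9 to 5.0% for the t-test and 5.0% for ANCOVA.

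| r | Width ratio, ANCOVA / t-test | Power at 25 points, t-test vs ANCOVA |
|---|---|---|
| 0.3 | 0.834 | 80% vs 92% |
| 0.5 | 0.895 | 91% vs 96% |
| 0.7 | 0.953 | 99% vs 99% |
| 0.87 | 0.999 | not run |

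Further results at r = 0.5, t-test vs ANCOVA:
- SD 16: mean width 29.6 vs 26.5 points; power 97.7% vs 99.3% at 30 points and 75% vs 84% at 20 points.
- SD 18: mean width 33.4 vs 29.8; power 84% vs 91% at 25 points.
- SD 14: power 96% vs 99% at 25 points.
- Equivalent size at SD 16: a t-test with 12 per arm has width 26.8 and power 95.6% at 25 points; ANCOVA with 10 per arm has 26.5 and 95.6%.

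**5. If 16 is instead held as the SD of change whatever r is.** The t-test has 91.0% power at 25 points. ANCOVA has 97.7%, 95.8%, 93.3% and 90.6% at r = 0.3, 0.5, 0.7 and 0.9.

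**6. Unequal SDs (assumed; baseline SD 16).** The SD of change is sqrt(s0² + s1² - 2 r s0 s1) and the ANCOVA residual SD is s1 x sqrt(1 - r²), where s0 and s1 are the baseline and Week 12 SDs. The least favourable case for ANCOVA is a true slope r x s1/s0 of exactly 1. Both SDs are then equal, and ANCOVA loses only the cost of estimating the slope.
- Week 12 SD 20: slope 1 at r = 0.8, where both SDs are 12; simulated widths 22.2 (t-test) vs 23.0 (ANCOVA), ratio 1.033. Break-even is at r about 0.60.
- Week 12 SD 18: break-even at r about 0.70; maximum ratio 1.033.
- Week 12 SD 12.8: ratio 0.782 at r = 0.5 and never above 0.827.

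**7. Chance imbalance.** The standard error of the baseline difference is 16 x sqrt(2/10) = 7.2 points. At r = 0.5 an imbalance of one standard error shifts the change-score difference by (1 - 0.5) x 7.2 = 3.6 points. An imbalance at least that large, in either direction, arises in about a third of such trials.

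**The case against.** The t-test on change is a legitimate, prespecified choice for a pilot study, and the ANCOVA will be run anyway, so only their rank is disputed. At the plan's lead scenario (30 points, SD 16) the gain is only 97.7% to 99.3%. The 20-point case is not one of the plan's targets. The correlation of 0.5 is inferred from one SD serving two purposes, and at 0.7 the gain is slight. The widths are averages: in a single trial ANCOVA gives the wider interval about 20% of the time at r = 0.5 and 38% at r = 0.7. The efficacy analysis is governed by a document not seen here, which may already specify an adjusted model.

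All of this is correct, and it limits the weight of the point. It does not supply a reason for preferring the t-test, and the documents give none. The trade remains lopsided: about 10% narrower at r = 0.5, against about 3% wider in the least favourable setting. Producing the ANCOVA as a sensitivity analysis is not equivalent either, because 13.4 does not commit to reporting its treatment difference. The unseen document means the criticism stands against Protocol 13.4 and the supplied SAP only.

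**Conclusion.** The point holds as a recommended improvement, not as an error. With equal SDs at the two visits, ANCOVA gives the narrower expected interval for any baseline/Week 12 correlation below about 0.87. At 0.5 the interval is about 10% narrower, roughly the value of four more patients. The gain in power is modest at the differences in Table 1, and larger at SD 18 or if the true difference is below 25 points.

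This rests on approximate normality, a common slope in the two arms, and an assumed correlation. If the Week 12 SD is clearly above the baseline SD, break-even falls to about 0.60 to 0.70, with a loss of at most about 3% in width. Confidence is medium because the correlation is not documented.

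**What to change.** Make the ANCOVA with treatment and baseline Ki67 the primary analysis, in Protocol 13.4 and in the document governing the Ki67 analysis. Specify the adjusted treatment difference, its 95% confidence interval and p-value as the output, and keep the t-test as the sensitivity analysis. That document should also make clear that the no-testing statement in SAP 4.3 does not apply to Ki67. The change must be fixed before unblinding, which Protocol 7.7 places "after the statistical analysis plan (SAP) has been signed and the database has been locked".

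Table 1 can stay if it is labelled as power for the unadjusted comparison.

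As a supportive analysis only, add site and PPI dose as main effects, to match the stratified randomization. If the strata are balanced and not prognostic, this widens the interval by about 1% relative to ANCOVA. Under an assumed 16/4 site split with unbalanced strata the cost is about 7% (28.5 vs 26.6 at r = 0.5). At r = 0.7 that model is then wider than the t-test (23.5 vs 23.0), which is why it should not be primary. Baseline adjustment of the secondary change endpoints is optional, since no gain was quantified for them.

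The cost is a paragraph in each document and one error degree of freedom (18 to 17), with no new patients or measurements. A protocol edit is an amendment that goes to the IRBs (Protocol 14.1.3). Protocol 13.2 also allows departures from the planned analyses to be described in the SAP, which may be the shorter route.
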